5.1.4. Lost to Follow-up

If the subject cannot be reached for a follow-up visit, at least three telephone contacts (or attempts) should be made prior to recording a missed follow-up visit. The subject however remains in the study until the 1-year follow-up. The subject will only be considered as 'Lost to follow-up' if he/she cannot be reached for the final 1-year follow-up.

NOTE:

- More than three attempts can be made, but three is the minimum required.

- In the event contact with the subject cannot be established, the investigator will immediately contact the referring physician. If the referring physician has not had contact with the subject, information from the subjects identified point of alternative contact will be utilized.

5.10. Premature Termination or Suspension of the Study

The Sponsor may decide to suspend or prematurely terminate the clinical study in one or more investigation sites if e.g. information that the risk to the study subjects is higher than initially indicated becomes available.

In the case of an early termination of the study, the regulatory authority(ies) and ethic committee(s) (ECs) should be informed according to local and national regulations. The reasons for termination should be provided and documented. An appropriate schedule for termination will be instituted.

For patient safety reasons, patients already enrolled in the study will continue to be followed for the planned course of study described in this protocol.

Patients will be informed that the study has been prematurely terminated and about the reason for this termination.

5.11. Description of Assessments and CRFs

All data to be collected is described below.

Demographic Information

Demographics collected will include but are not limited to gender, height, weight, age and race (if permitted).

Medical History

Relevant medical history will be collected but are not limited to conditions as diabetes mellitus, atrial fibrillation, peripheral vascular disease, previous MI(s), previous PCI/CABG, congestive heart failure, renal insufficiency, hypertension, previous cerebrovascular event and history of malignancy.

Physical examination

The physical examination is to include evaluations of blood pressure and heart rate as appropriate for the subject's condition.

Medication review

Information regarding concomitant medication, clopidogrel, ticlopidine, prasugrel, ticagrelor, aspirin and oral anticoagulation medication use will be obtained.

12-Lead ECG

Information regarding Q-waves, bundle-branch block and atrial fibrillation will be obtained pre-procedure at 6-month and in case of a clinical event.

Laboratory Tests

Blood tests will be performed to collect information regarding full blood count, serum creatinine, HbA1c and lipid profile. Troponin will be collected at time points specified and in case of a clinical event.

Angiography and Intravascular ultrasound (IVUS)

At baseline (pre-and post-intervention), quantitative coronary angiography and HD IVUS imaging is mandatory as outlined in section 5.6 for all subjects and analyzed by Imaging Core Laboratory. In case of a clinical event an angiogram may also be acquired.

NOTE: It is left at the discretion of the physician and standard of care of hospital to perform coronary angiography at any time point or any other imaging.

Endpoint Collection

The following events will be adjudicated via the CEC:

- Death
- MI
- Any repeat revascularization
- Target lesion thrombosis (TLT)

5.12. Additional Case Report Forms

Adverse Events (AEs)

AE forms will document a description of the AE, onset date and duration, severity, seriousness, treatment, and relatedness. The form will also document whether the event was anticipated or unanticipated.

Study Exit Form

This form will document termination of each subject's study participation and capture the reason for study exit.

NOTE: screen failures will not be captured into the eCRF.

Protocol Deviation Form

This form will document deviations from the study protocol.

6. Safety Reporting

6.1. Definition of Adverse Events (AEs)

The following definitions are from ISO 14155:2011.

Adverse Events (AEs)

Table 2. Classification of AEs

Non-serious	Adverse Event (AE) (includes all categories)
Serious	Serious Adverse Event (SAE) (includes all categories that are serious)

Adverse Event (AE)

An AE is defined as any untoward medical occurrence, unintended disease or injury, or untoward clinical signs (including abnormal laboratory findings) in subjects, users, or other persons.

Exceptions include events that are pre-existing (prior to index-procedure) and have not changed in severity or intensity. Once a pre-existing complication or event has changed in severity or intensity, it should be reported as an AE.

Serious Adverse Event (SAE)

A SAE is defined as an AE that:

- a. Led to a death, injury or permanent impairment to a body structure or a body function.
- b. Led to serious deterioration in the health of the subject, that either resulted in
 - i. a life-threatening illness or injury, or
 - ii. a permanent impairment of a body structure or a body function, or
 - iii. in-patient or prolonged hospitalization, or
 - iv. medical or surgical intervention to prevent life-threatening illness or injury or permanent impairment to a body structure or a body function,
- c. Led to foetal distress, foetal death or a congenital abnormality or birth defect.

NOTE: Planned hospitalization for a pre-existing condition, or a procedure required by the CIP, without serious deterioration in health, is not considered a SAE/AE.

Adverse Event (AE) Assessment and Reporting

As all devices used in this study are CE-mark approved and will only be used within the remit of their license, only adverse events, which in the opinion of the investigator, may represent a severe adverse advent, need to be reported.

Each AE record must include a description of the event, date of onset, date investigator (or designee) became aware of AE, resolution, severity, action taken, relationship to procedure and seriousness criteria.

Each AE must be recorded separately (each medical condition or symptom if no diagnosis is made).

Severity will be assessed by the investigator using the following definitions:

- Mild: asymptomatic or mild symptoms; clinical or diagnostic observations only; intervention not indicated.
- Moderate: minimal, local, or noninvasive intervention indicated; limiting
- Severe: medically significant but not immediately life-threatening; hospitalization or prolongation of hospitalization indicated; disabling

Relationship to the study procedure or algorithm will be assessed by the investigator for each AE using the following definitions (according to EU MDR 2017/745 and MEDDEV 2.7/3 revision 3):

1. Not related: the relationship to the algorithm or procedures can be excluded when:
 - The event is not a known side effect of the study algorithm or procedure.
 - The event has no temporal relationship with the study algorithm or procedure.
 - The event is biologically implausible.
 - The event involves a body-site, or an organ not expected to be affected by the study algorithm or procedure.
 - The event can be attributed to another cause (e.g. an underlying or concurrent illness/clinical condition, an effect of another device, drug, treatment or other risk factors).
 - The event does not depend on a false result given by the study algorithm or procedure used for diagnosis, when applicable.
 - Harms to the subject are not clearly due to use error.
 - In order to establish the non-relatedness, not all the criteria listed above might be met at the same time, depending on the type of procedures and the event.

2. Unlikely: the relationship with the use of the study algorithm or procedure seems not relevant and/or the event can be reasonably explained by another cause, but additional information may need to be obtained.
3. Possible: the relationship with the use of the study algorithm or procedure is weak but cannot be ruled out completely. Alternative causes are also possible (e.g. an underlying or concurrent illness/clinical condition or/and an effect of another device, drug or treatment). Cases where relatedness cannot be assessed, or no information has been obtained should also be classified as 'possible'.
4. Probable: the relationship with the use of the study algorithm or procedure seems relevant and/or the event cannot be reasonably explained by another cause, but additional information may need to be obtained.
5. Causal relationship: the event is associated with the study algorithm or procedure is beyond reasonable doubt when:
 - The event has a temporal relationship with the study algorithm or procedure.
 - The event follows a known response pattern to the study treatment algorithm or procedure (if the response pattern is previously known).
 - Other possible causes (e.g. an underlying or concurrent illness/clinical condition or/and an effect of another device, drug or treatment) have been adequately ruled out.
 - Harm to the subject is due to error in the use of the study algorithm or procedure.
 - The event depends on a false result given by the study algorithm or procedure used for diagnosis, when applicable.
 - In order to establish the relatedness, not all the criteria listed above might be met at the same time, depending on the event.

Seriousness: If the AE meets any of the SAE criteria mentioned in section 0 it is regarded as serious.

6.2. Reporting and Documentation

All SAEs that occur either during the index procedure (after calcium modification) or during the 1-year follow-up phase of the study will be documented as described above and entered into the eCRF as soon as possible upon knowledge of the event.

6.2.1. *Report by the investigator to the Sponsor*

The Principal Investigator (or designee) shall report all AEs to the Sponsor, or in case of discrepancy according to national regulations.

SAEs must be reported to the Sponsor immediately but in any event no later than 3 calendar days of occurrence or of the time the investigator becomes aware of the event. All information on the AE form must be made available to the Sponsor as early as possible.

The Investigator is responsible for reporting all SAEs and new findings/updates in relation to already reported events to the EC if required by national regulations or by the EC according to local regulations.

In case of early termination of the study, further follow-up of the study subject shall proceed according to this study protocol.

Further details regarding safety definitions and reporting are described in study safety plan.

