FIGURE 1a: PROPOSED CALCIUM MODIFICATION ALGORITHM

CYCLOPES treatment algorithm

Set Up

1. Cross the calcified lesion(s) with a coronary guidewire
2. Pass the imaging catheter through the lesion
3. If the imaging catheter does not pass, pre-dilate with angioplasty balloon(s) and re-attempt
4. For balloon uncrossable lesions, up-front rotational/orbital atherectomy may be required

Step 1. Define

Perform IVUS to define lesion(s) morphology/morphologies

[figure not shown]
Step 2. Modify

Modify lesion(s) based on calcium morphology

Step 3. Confirm

[figure not shown]
Repeat IVUS to confirm calcium is modified sufficiently to allow for stent implantation and final IVUS post stent insertion to ensure optimal stent implantation criteria are met

IVUS measurements must be obtained using a transducer frequency of ≥ 40 MHz with standard automated pullback speed of 0.5-1 mm/s

Figure 1a CYCLOPES calcium modification algorithm, summary version including set-up. The proposed algorithm uses the acronym DMC (Define, Modify, Confirm) to outline the steps to successful calcium modification. Step 1: Define, involves intravascular ultrasound to define the characteristics of the calcified lesion. Step 2: Modify involves the use of calcium modification devices to modify the calcified lesion. Step 3: Confirm requires a repeat intravascular ultrasound acquisition to confirm whether the modification process was successful or not. Dependent on the outcome of the confirm step, a recommendation to insert a stent or repeat calcium modification is made.

FIGURE 1b: PROPOSED CALCIUM MODIFICATION ALGORITHM

* Refer to the IVUS 1 2 3 Essentials Pre-stent Workflow.

† Cutting balloon size should be chosen as 0.5mm smaller than RVD (media-to-media measurement) of the vessel size as determined by intravascular imaging. It is strongly recommended that cutting balloon therapy be delivered to the target lesion at high pressure (e.g., 18-20 atmospheres) as this has been shown to be safe and effective in prior studies.

‡ Calcium morphology may be heterogenous, device selection at operator discretion.

Figure 1b CYCLOPES calcium modification algorithm. Detailed version.

FIGURE 1c: PROPOSED CALCIUM MODIFICATION ALGORITHM

[figure not shown]
[figure not shown]
[figure not shown]
CYCLOPES treatment algorithm		
 Circumferential calcium	 Frame 2216	Circumferential calcium: bright calcium echoes with acoustic shadowing in a circumferential pattern

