1.3. Study Objective

The aim of this study is to validate a comprehensive and intravascular imaging-based calcium modification algorithm for the treatment of moderate to severely calcified coronary lesions.

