5.8. Unscheduled Visit

Investigators may see the subjects, at their professional discretion, outside of the visits described in the study protocol. If an SAE is reported during an unscheduled visit, the SAE and its treatment (CABG, re-PCI if any) should be documented in the same manner as for a study visit, per section 6.2. No additional data collection or CRFs are required at the unscheduled visit.

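### Section 6.2 requires eCRF documentation of index-procedure SAEs only after calcium modification, so read literally it omits the Modify step under validation and conflicts with 6.2.1

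*Protocol*

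**What the plan says.** The protocol (section 1.3) states the purpose: "The aim of this study is to validate a comprehensive and intravascular imaging-based calcium modification algorithm". Section 6.2 then says which serious events must be documented and entered in the eCRF: "All SAEs that occur either during the index procedure (after calcium modification", and those in the 1-year follow-up.

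Section 6.2.1, directly below, governs reporting to the sponsor. The site's principal investigator "shall report all AEs to the Sponsor", and "SAEs must be reported to the Sponsor immediately but in any event no later than 3 calendar days of occurrence" or of the investigator's becoming aware. Neither sentence refers to a step of the procedure.

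Other sections show that harms of the modification phase are meant to be assessed. Section 6.1 asks the investigator to judge each AE for its relationship to the procedure or the algorithm. Section 7.1 lists potential AEs of the calcium modification devices, among them perforation, rupture, dissection, ventricular fibrillation and death. Appendix A counts an angiographic perforation whenever in the procedure it is detected.

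**The concern.** The documentation rule starts after the phase of most interest. Atherectomy, lithotripsy and cutting-balloon work take place in the Modify step, and atherectomy or predilatation may already be needed at set-up (5.6.3). A site that applies 6.2 to the letter need not enter a serious event from these steps in the eCRF. A site that works from 6.2.1 would probably enter it. The eCRF safety record for the modification phase could then be incomplete, or differ between the 25 sites for reasons unrelated to patients or technique. The study has no DSMB (14.2), so this record is a main source for describing the procedural safety of the algorithm.

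**Working it through.** No figure is at issue, so the check compares the two rules along the procedure described in 5.6.3.

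| Part of the procedure | 6.2, eCRF documentation, read literally | 6.2.1, report to sponsor |
|---|---|---|
| Set-up: wire crossing, possible predilatation or atherectomy | not covered | covered |
| Define: first IVUS run | not covered | covered |
| Modify, first pass | not covered | covered |
| Modify, repeat pass | unclear | covered |
| Final Confirm, stenting, optimisation | covered | covered |
| Follow-up to 1 year | covered | covered |

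**Why the repeat pass is unclear.** Under 5.6.3, if IVUS shows no sign of modification, the operator returns to Modify. An event in the second pass comes after the first modification but before the last. Section 6.2 does not say which one counts.

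**Whether a milder reading removes the gap.** The parenthesis may have meant that documentation starts once modification begins. The text does not say so, and that reading would still leave out set-up. Enrolment does not explain the parenthesis either. Under 5.3 a patient becomes a subject once the angiographic criteria are confirmed. The screen-failure exit for crossing failure (5.9) is behind the patient once guidewire and IVUS catheter have crossed. A subject in the Modify step is therefore normally enrolled and past that exit, yet outside 6.2.

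**Which events are exposed.** Section 5.11 sends death, MI, any repeat revascularization and target lesion thrombosis to the CEC. Section 3.3.2 adds stroke, acute kidney injury and major bleeding as endpoints, and edge dissection enters through strategy success. Perforation is on neither list, nor is a dissection away from the stent edge or a serious arrhythmia. These depend mainly on the SAE record and on the periprocedural complications that 3.1 says will be collected.

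**Size.** The protocol gives neither a complication rate nor the share of events recorded by other routes. The bounds run from no SAE missing, if sites enter everything they report under 6.2.1, to every set-up and modification SAE missing from the eCRF.

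**The case against.** The best reply is that the protocol, read as a whole, already brings these events into the eCRF. Section 6.2.1 requires the report and the information on the AE form. Section 5.12 lists that form among the case report forms, with onset date and seriousness and no procedural cut-off. Section 11.1 says that all required data go into an eCRF. Section 6.2 prohibits nothing, so a site that records every SAE complies with both rules. A study safety plan, not seen here, may add detail. All of this stands, and it is why loss of data cannot be asserted. It does not make the two sections agree: 6.2 is the section that states the eCRF rule for SAEs, and it carries a limit that 6.2.1 lacks.

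A reader might infer three stronger things that the protocol does not support.

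- That 6.1 fixes the start of SAE documentation at the index procedure. It says "Exceptions include events that are pre-existing (prior to index-procedure) and have not changed in severity or intensity". That wording is not exhaustive, the section adds a further exclusion for planned hospitalization, and it defines an AE rather than setting a documentation window.
- That the share of algorithm steps outside 6.2 measures the effect. Counting steps says nothing about how many SAEs are affected, and a repeat Modify pass may fall inside the rule.
- That SAE data are in fact being lost, or that the co-primary endpoints are affected. MSA comes from the imaging core laboratory and TLF from adjudicated events.

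**Conclusion.** The inconsistency is real and should be fixed. Section 6.2 states a cut-off that 6.2.1 does not share, and places it after the step under validation. The wording mismatch is certain. The consequence is a possible gap, or a difference between sites, in the eCRF record of serious modification-phase harms that are not endpoints. Its size cannot be computed from the protocol. The conclusion assumes that sites may apply 6.2 as written and that the safety plan does not already override it. Neither co-primary endpoint depends on this point.

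**What to change.** Delete the parenthesis in 6.2 and use one SAE window in 6.2 and 6.2.1 that covers the whole index procedure, including set-up and modification. State the start point explicitly and reconcile it with three places:

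- enrolment in 5.3;
- guidewire crossing as an inclusion criterion in 4.2.1;
- Appendix A, where PCI begins when the guidewire crosses the first lesion, whereas 5.6.1 places anticoagulation and baseline angiography earlier in the index procedure.

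Two separate minor points can be settled in the same amendment and add no weight to the main one.

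1. State where SAEs are recorded for patients classed as screen failures after wiring, predilatation or atherectomy. Section 5.9 has their data collected and the patient exited at once, and 5.12 keeps screen failures out of the eCRF. The Screened set in 8.2 holds subjects who had the index procedure, are in the eCRF and are followed to discharge. It is unclear whether these patients belong to it.
2. Align the reporting scope. Section 6.1 says that "only adverse events, which in the opinion of the investigator, may represent a severe adverse advent, need to be reported", probably a slip for a serious event, while 6.2.1 asks for all AEs.

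The cost is wording in 6.2 and 6.2.1 and, for the minor points, in 6.1, 5.9, 5.12 and 8.2, plus a few more SAE forms. If enrolment has started, set-up and modification SAEs would have to be entered retrospectively from source records. No new patient procedures are needed.

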7. RISKS EVALUATION

7.1. *Potential adverse events (AEs)*

The potential AEs that may be associated with the use of a calcium modification devices including non-compliant balloons, rotational atherectomy devices, intravascular lithotripsy devices and cutting angioplasty balloons in native coronary arteries include, but not limited to, are listed below.

• Haematoma at the vascular access site• Pseudoaneurysm• Acute myocardial infarction• Pulse arrhythmia• Angina pectoris• Arterial perforation• Spasm of coronary arteries• Death• Cerebral circulatory disorders• General bleeding	
• Side effects due to the accompanying medication• Thrombus formation• Arterial rupture• Dissection of the coronary vessel• Hypotension• Ventricular fibrillation• Ischaemia• Arterio-venous fistulas• Palpitations• Vascular complications which necessitate a surgical intervention	
• Infections• Vessel trauma requiring surgical repair or re-intervention• Emergent Coronary Artery Bypass Graft Surgery (CABG)• Arrhythmia, including ventricular fibrillation• Total occlusion of a coronary artery• Restenosis of prior treated target vessel segment
---	--	--

7.2. Methods to Minimize Risks

Several procedures have been incorporated into this protocol to protect study subjects.

- Specific inclusion/exclusion criteria ensure that patients at increased risk are not enrolled in the study (e.g. patients presenting with cardiogenic shock, ACS or left main stenosis).
- Study subjects will be closely monitored post-procedure to detect and capture events.
- Qualified physicians will participate as investigators and have experienced staff to perform.

8. Statistical Consideration/Evaluation

8.1. Statistical Considerations and Analysis

The statistical analysis plan will be finalized prior to data freeze and will include an in-depth technical description of the statistical analyses described in this section. This section provides a summary of the planned statistical analyses of primary endpoints and key secondary endpoints as listed in section 3.3.

8.2. Analysis sets

Screened set

All potentially eligible subjects meeting the general inclusion and exclusion criteria, who have signed an informed consent form, have had the index procedure and have been entered into the eCRF will be included in this set. These subjects will be followed up until discharge. This set also includes subjects who complete 12 months of follow up.

Full analysis set (FAS)

This set includes all subjects who have signed an informed consent form, have been entered into the eCRF, have had the index procedure completed and have met all inclusion and exclusion criteria. These subjects will have been assessed using the CYCLOPES calcium modification algorithm and will have been followed up to the end of study (12 months).

Per protocol set (PP)

This set will include all subjects from the FAS who have had no major protocol deviations. As outlined in section 11.3.

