5.9. Subject Discontinuation

Subjects will participate in the study until they complete the 12-month post treatment assessments (per protocol). Subjects who do not complete the study per protocol may be withdrawn from the study in the following manner:

5.1.1. *Withdrawal prior and/or during index procedure*

Patients who have signed an informed consent form, but that are screen failures, will be documented as such on the subject screening log.

For patients who were declared eligible for the study but who are discontinued for any reason,

- either, prior to the commencement of PCI procedure or,
- during the procedure, as it was not possible to cross the lesion with either the guidewire or the HD IVUS catheter.

These patients will also be considered screen failures. Data until that period will be collected and the patient will be immediately exited from study. The reason for the early withdrawal must be documented in the subject screening log.

Patients that have not passed screening will not be enrolled in the study and further follow-up of these patients shall proceed according to the hospital standard procedures.

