8.3.3. Primary analysis

The study will have co-primary endpoints. The co-primary endpoints are minimum stent area (MSA) at the site of maximum calcification measured at the end of the index procedure and target lesion failure (TLF) defined as the composite of cardiac death, non-fatal myocardial infarction related to the target vessel, and unplanned ischemia-driven target lesion revascularization at one-year post-procedure. MSA is a numerical measurement in millimeters, measured at the independent imaging core laboratory. TLF is a binary endpoint (TLF or no TLF).

The primary analysis will be conducted on the FAS and will estimate the proportion of TLF at 1-year with corresponding exact two-sided 95% CI. Descriptive analyses for MSA will be performed.

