8.3.5. CIP deviations

Major CIP deviations are deviations from the CIP which potentially could have a meaningful impact on study conduct, or on the primary or secondary outcomes for an individual subject. The criteria for identifying major CIP deviations will be defined within the appropriate CIP-specific document at study start. Major CIP deviations will be reviewed as part of the ongoing data cleaning process and all-important deviations will be identified and documented prior to database lock to confirm inclusion or exclusion from analysis sets. The analysis will be conducted on the FAS.

CIP deviations will be summarized for all deviations and by type, with event counts and number of subjects with at least one deviation.

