11.3. Protocol Deviations

Investigators are not allowed to deviate from this CIP without prior authorization by the Sponsor except under emergency situations when necessary to preserve the rights, safety or well-being of study subjects.

Deviations and non-compliances will be recorded together with an explanation. Deviations or non-compliances that impact the rights, welfare, or safety of subjects shall be reported as soon as possible to the Sponsor and IEC, as required.

If appropriate, corrective, and preventive actions will be discussed by the Sponsor, investigator, and/or the IEC to determine a suitable course of action.

Deviations include, but are not limited to the following list:

- Failure to receive assigned treatment.
- Failure to obtain informed consent prior to conducting study specific activities.
- Inclusion/exclusion criteria not met.
- Incorrect version of the CIP/PIL used.
- Subject could not be reached for a follow-up visit or follow-up visit was outside window.
- AEs not reported by investigators in the required timeframe as specified in the protocol.
- Source data permanently lost.

Site compliance regarding deviations will be reviewed by the clinical study manager on a regular basis. In addition, all deviations from the protocol will be documented in the final report.

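### The primary analysis set is defined by having met every eligibility criterion, so treated patients found ineligible leave the 1-year TLF estimate, and on one reading their follow-up stops at discharge

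*Protocol*

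**What the plan says.** Protocol section 8.2 builds the FAS from patients with consent, an eCRF entry and a completed index procedure who "have met all inclusion and exclusion criteria" and have 12 months of follow-up. Section 8.3.3 then states: "The primary analysis will be conducted on the FAS and will estimate the proportion of TLF at 1-year with corresponding exact two-sided 95% CI".

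The per-protocol set is the FAS without major deviations, with a pointer to section 11.3. That section's list of deviations includes "Inclusion/exclusion criteria not met".

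The Screened set in 8.2 is wider. It takes consented patients who met the general criteria, had the index procedure and are in the eCRF. Of them it says: "These subjects will be followed up until discharge". The next sentence adds that the set also contains those who complete 12 months.

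On timing, section 8.3.5 says that "all-important deviations will be identified and documented prior to database lock to confirm inclusion or exclusion from analysis sets". It also says that the criteria for major deviations are set at study start and that review is part of ongoing data cleaning.

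On follow-up, section 5.9 keeps subjects in the study to the 12-month assessment, and section 6.2 collects serious adverse events over the 1-year follow-up.

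**The concern.** A full analysis set normally keeps everyone who entered and was treated; eligibility violations are handled in the per-protocol set. Here the eligibility filter already sits in the primary set. With no comparator and no hypothesis test, the TLF proportion is itself the clinical result, so the choice of who is in its denominator bears directly on the answer.

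The two ways out do different harm. Early exclusion, with follow-up ended at discharge, leaves 1-year TLF unobserved in patients who received the intervention, and no later sensitivity analysis can recover it. Late exclusion leaves the data in hand, but the decision can be made when the patient's outcome is known. The study is open-label, and eligibility here rests partly on judgement of calcium and stenosis.

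**Working it through.** **Passages side by side**

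1. *Same failure, two sets.* Section 11.3 classes an unmet criterion as a deviation, and 8.2 defines the per-protocol set by major deviations. Section 8.2 also makes meeting all criteria a condition of the FAS. A violator is therefore already out before the per-protocol filter is applied.

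2. *Does the discharge sentence reach treated patients?* The Screened set requires the index procedure and an eCRF entry, while section 5.12 keeps screen failures out of the eCRF. The sentence therefore cannot be about untreated screen failures alone. Read that way, it conflicts with 5.9 and 6.2.

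3. *When is membership settled?* Section 5.3 places the final eligibility check at the angiography. Section 8.3.5 has deviations "identified and documented prior to database lock to confirm inclusion or exclusion from analysis sets". Section 3.2 adds six months after follow-up for data freeze, core laboratory work and analysis, so lock comes after 12-month outcomes. Review may happen earlier, but nothing in 8.3.5 requires it.

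4. *Is the test itself fixed?* Section 8.2 does not say when, or on whose reading, the criteria count as met. The criteria also vary: the synopsis asks for documented ischaemia, 4.2.1 also admits symptoms and non-ST-elevation infarction, and 7.2 says acute coronary syndrome and left main stenosis are kept out, although 4.2.2 lists neither as such. These passages need reconciling.

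**Size**

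Section 8.4 gives a target of 500 with no expected TLF rate or precision, so there is no figure of the plan's to reproduce. Everything below except N = 500 is assumed.

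Inputs: overall TLF rate p; m patients removed, as fraction r = m/500; risk ratio k of removed to retained patients.

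- Retained risk: q = p / ((1 − r) + r·k)
- Events removed: x = m·k·q, rounded to whole events
- FAS estimate: (500p − x) / (500 − m), with exact 95% CI

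Keeping all 500 at p = 10%: 50/500 = 10.0% (CI 7.5 to 13.0, half-width about 2.7 points).

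Worked line, m = 25, k = 2: q = 0.10/(0.95 + 0.10) = 0.0952; x = 25 × 2 × 0.0952 = 4.8, taken as 5; 45/475 = 9.5%.

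| Removed | k | Events removed | FAS estimate | 95% CI | Change, points |
|---|---|---|---|---|---|
| 25 | 1 | 2 | 48/475 = 10.1% | 7.5 to 13.2 | +0.1 |
| 25 | 2 | 5 | 45/475 = 9.5% | 7.0 to 12.5 | −0.5 |
| 25 | 3 | 7 | 43/475 = 9.1% | 6.6 to 12.0 | −0.9 |
| 50 | 1 | 5 | 45/450 = 10.0% | 7.4 to 13.2 | 0.0 |
| 50 | 2 | 9 | 41/450 = 9.1% | 6.6 to 12.2 | −0.9 |
| 50 | 3 | 12 | 38/450 = 8.4% | 6.0 to 11.4 | −1.6 |

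The same grid (25 to 50 removed, k = 2 to 3) at other TLF rates:

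- p = 5%: estimates 4.84% down to 4.22%, a fall of 0.2 to 0.8 points.
- p = 15%: estimates 14.32% down to 12.44%, a fall of 0.7 to 2.6 points.

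With only 10 removed at p = 10%, the estimates are 9.8% (k = 2) and 9.6% (k = 3). The arithmetic limits for 25 removed at p = 10% are 50/475 = 10.5% (none had TLF) and 25/475 = 5.3% (all did). The bias can therefore run upward as well as downward.

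**The case against.** The other side has several good points.

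- *Core laboratories have no stated eligibility role.* A reader might infer that they re-judge eligibility, because they read the same baseline images. The protocol does not say so. Section 5.3 puts the check at the angiography, stenosis is a visual estimate in 4.2.1, and the footnote to Table 1 sends recordings for the stent-area endpoint. What stands is narrower: 8.2 does not say whose reading governs.
- *One patient cannot suffer both harms.* Someone followed only to discharge has no known 1-year TLF, and someone removed near lock already has 12-month data. These must be kept as two routes.
- *The deviation review has safeguards.* Its criteria are fixed at study start and it runs during data cleaning. This narrows the room for outcome-driven decisions but does not close it, because membership may still be confirmed up to lock.
- *Blinding of that review may be in the statistical analysis plan.* That plan is not at hand, so the lack of a blinding rule in the protocol is not counted as a fault. The FAS definition is stated in the protocol, and that is what is faulted.
- *The discharge sentence may be loose wording.* The Screened set also includes 12-month completers, and 5.3 reserves the word subject for enrolled patients, so 5.9 could be read as covering only those. That reading still leaves treated patients outside the FAS with follow-up ended at discharge, and it does not explain why they are in the eCRF when 5.12 keeps screen failures out.
- *The magnitude is assumed.* This is correct, and no pass/fail decision depends on it.

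**Conclusion.** The point holds in limited form. As written, 8.2 takes treated patients found ineligible out of the primary TLF analysis, duplicating an exclusion that belongs to the per-protocol set. The discharge sentence conflicts with 5.9 and 6.2.

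The documents do not show that TLF will be selected on outcome. They show a definition that permits it in late removals and loses the outcome in early ones. The size cannot be known from the protocol. The shift of about 0.5 to 1.6 points rests on an assumed 10% TLF, 5 to 10% of patients removed, and two to three times the risk in those removed. It is smaller than the sampling half-width of about 2.7 points, but it is bias and does not shrink with sample size. If removal is unrelated to risk, the shift is close to nil. The wording is worth changing because the remedy is cheap; the point does not invalidate the study.

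**What to change.** 1. In 8.2, define the FAS as all consented patients enrolled under 5.3, with eligibility as documented by the operator at the index angiography, in whom the index procedure was started. Reconcile this with the rule in 5.9 that makes screen failures of patients whose lesion the guidewire or IVUS catheter cannot cross: Appendix A starts PCI at guidewire crossing, so the two overlap for the IVUS catheter.
2. Keep eligibility violations found later in the FAS. Exclude them only from the per-protocol set, by a decision made without knowledge of TLF.
3. Delete the Screened-set sentence on follow-up to discharge, or reconcile it with 5.9 and 6.2, so that treated patients have 12-month outcome data. Limiting it to patients in whom PCI was not started would not work, because everyone in that set has had the index procedure.

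Cost: a wording change and a few more 12-month contacts. The FAS will contain a few patients who did not strictly meet the criteria; the per-protocol analysis shows whether they matter.
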